11.5. Records Retention and Study Files

11.5.1. Study Files and Retention of Records

The investigator must maintain adequate and accurate records to enable the conduct of the study to be fully documented and the study data to be subsequently verified. These documents should be classified into at least the following 2 categories: (1) investigator's study file and (2) patient clinical source documents.

The investigator's study file will contain the protocol/amendments, eCRF and query forms, IRB/IEC, and governmental approval with correspondence, ICF, drug records, staff curriculum vitae and authorization forms, and other appropriate documents and correspondence.

Patient clinical source documents (usually defined by the project in advance to record key efficacy/safety parameters independent of the eCRFs) would include (although not be limited to) the following: patient hospital/clinic records, physician's and nurse's notes, appointment book, original laboratory reports, ECG, electroencephalogram, x-ray, pathology and special assessment reports, consultant letters, screening and enrollment log, etc.

Following closure of the study, the investigator must maintain all study records in a safe and secure location. The records must be maintained to allow easy and timely retrieval when needed (eg, audit or inspection) and, whenever feasible, to allow any subsequent review of data in conjunction with assessment of the facility, supporting systems, and personnel. Where permitted by local laws/regulations or institutional policy, some or all of these records can be maintained in a format other than hard copy (eg, microfiche, scanned, or electronic); however, caution needs to be exercised before such action is taken. The investigator must ensure that all reproductions are legible, are a true and accurate copy of the original, and meet accessibility and retrieval standards, including regenerating a hard copy, if required. Furthermore, the investigator must ensure that there is an acceptable backup of these reproductions and that an acceptable quality control process exists for making these reproductions.

The sponsor will inform the investigator of the timeperiod for retaining these records to comply with all applicable regulatory requirements. The minimum retention time will meet the strictest standard applicable to that study center for the study, as dictated by any institutional requirements or local laws or regulations, or the sponsor's standards/procedures; otherwise, the retention period will default to 15 years.

The investigator must notify the sponsor of any changes in the archival arrangements, including but not limited to the following: archiving at an off-site facility and transfer of ownership of or responsibility for the records in the event that the investigator leaves the study center.

If the investigator cannot guarantee this archiving requirement at the study center for any or all of the documents, special arrangements must be made between the investigator and BeiGene to store these in sealed containers outside of the study center so that they can be returned sealed to the investigator in case of a regulatory audit. When source documents are required for the continued care of the patient, appropriate copies should be made for storage outside of the study center.

Biologic samples at the conclusion of this study may be retained in storage by the sponsor as outlined in the study manual.

11.5.2. Provision of Study Results and Information to Investigators

When the clinical study report is completed, the sponsor will provide the major findings of the study to the investigator.

In addition, details of the pamiparib assignment will be provided to the investigator to enable him/her to review the data to determine the outcome of the study for his/her patient(s).

The sponsor will not routinely inform the investigator or patient of the test results because the information generated from this study will be preliminary in nature and the significance and scientific validity of the results will be undetermined at such an early stage of research.

11.6. Information Disclosure and Inventions

All information provided by the sponsor and all data and information generated by the study center as part of the study (other than a patient's medical records) are the sole property of the sponsor.

All rights, title, and interests in any inventions, know-how, or other intellectual or industrial property rights that are conceived or reduced to practice by the study center personnel during the course of or as a result of the study are the sole property of the sponsor and are hereby assigned to the sponsor.

If a written contract for the conduct of the study that includes ownership provisions inconsistent with this statement is executed between the sponsor and the study center, that contract's ownership provisions shall apply rather than this statement.

All information provided by the sponsor and all data and information generated by the study center as part of the study (other than a patient's medical records) will be kept confidential by the investigator and other study center personnel. This information and data will not be used by the investigator or other study center personnel for any purpose other than conducting the study without the prior written consent of the sponsor.

These restrictions do not apply to:

- Information that becomes publicly available through no fault of the investigator or study center personnel

- Information that is necessary to disclose in confidence to an IEC/IRB solely for the evaluation of the study
- Information that is necessary to disclose to provide appropriate medical care to a patient
- Study results that may be published as described in [Section 11.3.2](#).

If a written contract for the conduct of the study that includes provisions inconsistent with this statement is executed, that contract's provisions shall apply rather than this statement.

11.7. Joint Investigator/Sponsor Responsibilities

11.7.1. Access to Information for Monitoring

In accordance with International Council for Harmonisation Good Clinical Practice guidelines, the study monitor must have direct access to the investigator's source documentation to verify the data recorded in the eCRFs for consistency.

The monitor is responsible for routine review of the eCRFs at regular intervals throughout the study to verify adherence to the protocol and the completeness, consistency, and accuracy of the data being entered on them. The monitor should have access to any patient records needed to verify the entries on the eCRFs. The investigator agrees to cooperate with the monitor to ensure that any problems detected in the course of these monitoring visits are resolved.

11.7.2. Access to Information for Auditing or Inspections

Representatives of regulatory authorities or of BeiGene may conduct inspections or audits any time during or after completion of this clinical study. If the investigator is notified of an inspection by a regulatory authority the investigator agrees to notify the sponsor or its designee immediately. The investigator agrees to provide to representatives of a regulatory agency or BeiGene access to records, facilities, and personnel for the effective conduct of any inspection or audit.

11.7.3 Publication Policy

The results of this study will be published or presented at scientific meetings in a timely, objective, and clinically meaningful manner that is consistent with good science, industry and regulatory guidance, and the need to protect the intellectual property of BeiGene (sponsor), regardless of the outcome of the study. The data generated in this clinical study are the exclusive property of the sponsor and are confidential. For multicenter studies, the first publication or disclosure of study results shall be a complete, joint multicenter publication or disclosure coordinated by the sponsor. Thereafter, any secondary publications will reference the original publication(s). Authorship will be determined by mutual agreement and all authors must meet the criteria for authorship established by the International Committee of Medical Journal Editors Uniform Requirements for Manuscripts or stricter local criteria (International Committee of Medical Journal Editors 2016).

After conclusion of the study and without prior written approval from BeiGene, investigators in this

study may communicate, orally present, or publish in scientific journals or other scholarly media only after the following conditions have been met:

- The results of the study in their entirety have been publicly disclosed by or with the consent of BeiGene in an abstract, manuscript, or presentation form; or
- The study has been completed at all study sites for the earlier of: at least 2 years or the period indicated in the clinical study agreement.
- No such communication, presentation, or publication will include BeiGene's confidential information.
- Each investigator agrees to submit all manuscripts or congress abstracts and posters/presentations to the sponsor prior to submission in accordance with the clinical study agreement. This allows the sponsors to protect proprietary information, provide comments based on information from other studies that may not yet be available to the investigator, and ensure scientific and clinical accuracy. The details of the processes of producing and reviewing reports, manuscripts, and presentations based on the data from this trial will be presented in the investigator's clinical study agreement. Each investigator agrees that, in accordance with the terms of clinical study agreement, a further delay of the publication/presentation may be requested by the sponsor to allow for patent filings and/or protection in advance of the publication/presentation.

13. APPENDICES

APPENDIX 1. SCHEDULE OF ASSESSMENTS

Study Phase	Pre-screening ^a	Screening ^a	Treatment ^b					Un-scheduled Visit ^c	End-of-Treatment (EOT) Visit ^d	Safety Follow-up ^e	Long-term Follow-up ^f
			Cycle 1		Cycle 2		Cycle ≥3				
			Day 1	Day 15	Day 1	Day 15	Day 1				
Allowed time window				± 2	± 3	± 3	± 5				
Study Day	≤ 28	-28 to -1	1	15	29	43	57, 85, etc.	Varies	Varies	Varies	Varies
Informed consent	X	X									
Eligibility criteria		X									
Demographics, medical history, smoking history		X									
Complete physical examination		X							X		
Limited physical examination			X	X	X	X	X	X			
Vital signs and weight ^g		X	X	X	X	X	X	X	X		
Height		X									
ECOG performance status		X	X		X		X	X	X		
12-lead ECG ^h		X (-14 to -1)	X	X	X	X	X	X	X		
Hematology ⁱ		X (-14 to -1)	X	X	X	X	X	X	X	X	
Chemistry ⁱ		X (-14 to -1)	X	X	X	X	X	X	X	X	
Urinalysis ⁱ		X (-14 to -1)	X					X	X		
HBV/HCV tests ^j		X	As clinically indicated								
BPI-SF and EQ-5D-5L questionnaires			X		X		X		X		
PSA levels ^k		X	X		X		X (q4w ± 7d)	X	X		X (q4w ± 7d)
Testosterone ^w	X	X							X		

APPENDIX 1. SCHEDULE OF ASSESSMENTS

Study Phase	Pre-screening ^a	Screening ^a	Treatment ^b					Un-scheduled Visit ^c	End-of-Treatment (EOT) Visit ^d	Safety Follow-up ^e	Long-term Follow-up ^f
			Cycle 1		Cycle 2		Cycle ≥3				
			Day 1	Day 15	Day 1	Day 15	Day 1				
Allowed time window	≤ 28	-28 to -1		± 2	± 3	± 3	± 5				
Study Day	≤ 28	-28 to -1	1	15	29	43	57, 85, etc.	Varies	Varies	Varies	Varies
CT with intravenous contrast of chest, abdomen and pelvis ^l		X					X (q8w ± 7d for 24 weeks, then q12w ± 7d)	X	X		X (~q12w)
Bone scan ^m		X					X (q8w ± 7d for 24 weeks, then q12w ± 7d)	X	X		X (~q12w)
MRI scan of brain, if clinically indicated ⁿ		X						X			
Patient treatment authorization		X ^a									
Pamiparib			Twice a day dosing continuously								
Pamiparib dispensing/accountability			X		X		X	X	X		
Adverse events ^o		X	X	X	X	X	X	X	X	X	X
Concomitant medication(s) ^p		X	X	X	X	X	X	X	X	X	X (~q12w)
Pharmacokinetics ^q			X	X							
Blood sample for CTCs ^r	X	X	X				X (q8w ± 7d for 24 weeks, then q12w ± 7d)		X		

APPENDIX 1. SCHEDULE OF ASSESSMENTS

Study Phase	Pre-screening ^a	Screening ^a	Treatment ^b					Un-scheduled Visit ^c	End-of-Treatment (EOT) Visit ^d	Safety Follow-up ^e	Long-term Follow-up ^f
			Cycle 1		Cycle 2		Cycle ≥3				
			Day 1	Day 15	Day 1	Day 15	Day 1				
Allowed time window	≤ 28	-28 to -1		± 2	± 3	± 3	± 5				
Study Day	≤ 28	-28 to -1	1	15	29	43	57, 85, etc.	Varies	Varies	Varies	Varies
Blood sample for biomarkers ^s			X				X (q8w ± 7d for 24 weeks, then q12w ± 7d)		X		
Archival tumor tissue ^t		X									
Fresh tumor tissue (additional consent required) ^u		X							X		
Survival follow-up ^v											X (~q12w)

Abbreviations: -7/-14/-28 to -1, Day -7/-14/-28 to Day -1 of screening; AE, adverse event; BPI-SF, Brief Pain Inventory Short Form; CT, computed tomography; CTC, circulating tumor cell; ECG, electrocardiogram; ECOG, Eastern Cooperative Oncology Group; EOT, End-of-Treatment; EQ-5D-5L, European Quality of Life 5-Dimensions 5-Levels Health Questionnaire; HBV, hepatitis B virus; HCV, hepatitis C virus; HRD, homologous recombination deficiency; MRI, magnetic resonance imaging; PARP, poly (ADP-ribose) polymerase; PCWG3, Prostate Cancer Clinical Trials Working Group 3; PD, progressive disease; PK, pharmacokinetic; PSA, prostate-specific antigen; q4w ± 7d, every 4 weeks ±7 days; q8w ± 7d, every 8 weeks ±7 days; ~q12w, approximately every 12 weeks; SAE, serious adverse event.

- Pre-screening for prospective testing of CTC-HRD status (blood sample) can be completed before the study eligibility screening. A separate pre-screening informed consent must be obtained. Screening must occur within 28 days before Day 1. Some assessments have a narrower screening window as shown in the table. Assessments obtained within 7 days of Day 1 do not have to be repeated on Day 1. Patient treatment authorization may occur as late as Day 1 before the first dose of pamiparib.
- Patients must initiate study treatment within 4 days after authorization for treatment. Administration of pamiparib will continue until PD, as assessed by investigator per PCWG3 criteria, unacceptable toxicity, death, or another discontinuation criterion is met (Sections 5.5.1 and 5.6.4. A cycle is 28 days. Assessments shown for Cycle 3 apply to all subsequent cycles, unless noted otherwise.
- Unscheduled visits may occur at any time as necessary as per investigator decision or patient’s request for reasons such as assessment or follow-up of AEs. Study assessments of an unscheduled visit, as indicated by ‘X,’ should be performed based on the reason for the unscheduled visit. If PD is suspected, imaging studies should be performed and blood for biomarkers should be obtained as appropriate.

- d. The EOT Visit should occur within 7 days after pamiparib has been permanently discontinued. A visit should be scheduled as soon as possible, but the EOT Visit may occur later after discussion with the medical monitor for specific circumstances, such as prolonged hospitalization. The visit at which tumor assessments showed PD may be used as the EOT Visit if all required assessments were performed. Tumor assessments do not have to be repeated if they were performed within 14 days of the EOT Visit or at a prior response evaluation that documented PD. An ECG does not have to be repeated if it was performed within 14 days of the EOT Visit.
- e. Approximately 30 days after the last dose of pamiparib or before initiation of new anticancer therapy, whichever occurs first, the Safety Follow-up Visit will occur with the outlined safety assessments. If new anticancer therapy is inadvertently initiated before the Safety Follow-up Visit, (eg, without the knowledge of the study center team), a Safety Follow-up Visit should be scheduled as soon as possible. For patients who do not want to or cannot return to the clinic for the Safety Follow-up Visit, the patient should be contacted by telephone for a review of AEs. If these attempts of contact are unsuccessful, the additional attempts detailed in [Section 5.6.3](#) should be made.
- f. Patients will be followed for survival and initiation of new anticancer therapy via telephone contact or other means (eg, clinic visit) approximately every 12 weeks.
Patients who were permanently discontinued from pamiparib for reasons other than PD and meet criteria otherwise (eg, discontinued for AE and no new anticancer therapy) will be followed with tumor and PSA assessments every 12 weeks and 4 weeks (± 7 days), respectively, until PD or any other reason listed in [Section 5.6.4](#), whichever occurs first. For efficacy assessments as per protocol, refer to [Section 7.3](#). If the patient refuses to return for these PSA and tumor assessments or is unable to do so, every effort should be made to contact the patient by telephone to determine the patient's disease status and survival.
Should attempts of telephone contact be unsuccessful, the additional attempts detailed in [Section 5.6.3](#) should be made. If a patient cannot be contacted despite all attempts, the patient will be considered lost to follow-up.
- g. Vital signs (systolic and diastolic blood pressure; pulse rate; and oral, temporal, tympanic, or armpit temperature) will be measured before pamiparib administration and approximately 15 minutes before each collection of PK blood samples, if applicable, during the treatment phase.
- h. ECGs will be obtained approximately every 28 days and at each subsequent visit including EOT. Additional ECGs will be performed, if clinically indicated.
- i. Hematology includes hemoglobin, platelet count, white blood cell count, neutrophil count, and lymphocyte count.
Chemistry includes albumin, alkaline phosphatase, alanine aminotransferase, aspartate aminotransferase, blood urea nitrogen, chloride, creatinine, glucose, lactate dehydrogenase, phosphate, potassium, sodium, total bilirubin, and total protein.
Urinalysis includes blood, glucose, ketones, protein, red blood cells, and white blood cells.
- j. Testing will be performed by a central laboratory and/or the local laboratory at screening and as clinically indicated and will include HBV/HCV serology (hepatitis B surface antigen, hepatitis B surface antibody, hepatitis B core antibody, and HCV antibody) and viral load assessment (HBV DNA and HCV RNA).
- k. PSA levels will be assessed during screening, on Day 1, and every 4 weeks (± 7 days), or as clinically indicated. Responses by PCWG3 criteria must be confirmed ≥ 3 weeks later. Patients without PD at the EOT Visit should be followed with PSA assessments every 4 weeks (± 7 days) during the long-term follow-up phase.
- l. Following the screening tumor assessment, tumor assessments will occur at the schedule of every 8 weeks (± 7 days) after Day 1 for the first 24 weeks, then at the schedule of every 12 weeks (± 7 days). Any measurable disease must be documented at screening and reassessed at each subsequent tumor evaluation. The same imaging method(s) used at screening must be used throughout the study. A documented standard-of-care tumor assessment may be used as the screening assessment provided it meets protocol requirements ([Section 7.3.1.2](#)). CT scan with intravenous contrast is the preferred imaging method for assessment of chest, abdomen, and pelvis. Other imaging methods are allowed as outlined in [Section 7.3.1.2](#). Imaging of other areas of disease should be performed every 8 weeks ± 7 days for 24 weeks, then every 12 weeks ± 7 days. Patients without PD at the EOT Visit should be followed with tumor

assessments every 12 weeks (± 7 days) during the long-term follow-up phase.

- m. Whole-body radionuclide bone scan must be performed at screening and will then occur at the schedule of every 8 weeks (± 7 days) after Day 1 for the first 24 weeks, then at the schedule of every 12 weeks (± 7 days). Patients without PD at the EOT Visit should be followed with bone scans every 12 weeks (± 7 days) during the long-term follow-up phase.
- n. MRI scan of the brain to assess for brain metastases must be performed at screening if the patient has symptoms that could be due to brain metastases. CT scan with intravenous contrast is acceptable if MRI is not available or the patient is claustrophobic. If brain metastases are present at baseline, the patient is eligible for this study if criteria listed under Exclusion Criterion 8 are met.
- o. AEs and laboratory safety measurements will be recorded at each study visit, graded per National Cancer Institute-Common Terminology Criteria for Adverse Events Version 4.03 or higher, and assessed as outlined in [Section 9](#). After the informed consent form has been signed, but before initiation of pamiparib, only SAEs should be reported. After initiation of pamiparib, all AEs and SAEs, regardless of relationship to pamiparib, will be reported until 30 days after last dose of pamiparib or initiation of new anticancer therapy, whichever occurs first. After this period, the investigator should report any SAEs that are believed to be related to pamiparib.
- p. All concomitant medications taken by or administered to the patient within 28 days before Day 1 and 30 days after the last dose of pamiparib will be recorded. Concomitant medications include new anticancer therapy information acquired during the long-term follow-up phase.
- q. PK samples for pamiparib will be collected at various timepoints at all non-China centers and at centers with such capability in China. PK samples will be collected from patients at the following timepoints: predose (within 30 minutes before dose) and 2 hours (± 30 minutes) postdose on Cycle 1 Day 1 and Cycle 1 Day 15. The time of pamiparib administration on the day before Day 15 must be recorded on the electronic case report form. Details concerning collection, handling, and processing of the PK plasma samples will be provided in the laboratory manual.
- r. One blood sample (10 mL) must be collected for prospective testing of CTC-HRD status and CTC enumeration during pre-screening or screening. Blood samples (10 mL each) will then be collected every 8 weeks (± 7 days) after Day 1 for the first 24 weeks, then at the schedule of every 12 weeks (± 7 days), as well as at the EOT Visit (unless they had been collected within 14 days). Instructions for the processing, storage, and shipping of samples will be provided in the study manual.
- s. One blood sample (8 mL) must be collected before initiation of pamiparib on Day 1 of Cycle 1 for the assessment of BRCA1/2 germline mutations. Two blood samples (10 mL each) will be collected for the assessment of plasma biomarkers of PARP inhibitor response/resistance before pamiparib administration every 8 weeks (± 7 days) after Day 1 for the first 24 weeks, then at the schedule of every 12 weeks (± 7 days), as well as at the EOT Visit (unless they had been collected within 14 days). Instructions for the processing, storage, and shipping of samples will be provided in the study manual.
- t. Archival tumor tissue, if available, shall be sent to the central laboratory testing for retrospective analysis of HRD mutational status.
- u. In the absence of archival tumor tissues, a fresh baseline biopsy of a tumor lesion is highly recommended. Written patient consent is required for fresh tumor biopsies. Optional biopsy will also be taken, if agreeable, at the EOT Visit for patients who have confirmed PD during the study from accessible tumor sites to obtain samples to explore resistance mechanism. If feasible, any follow-up biopsy should, ideally, be taken from the same tumor lesion as the baseline biopsy.
- v. Patients will be followed for survival via telephone contact approximately every 12 weeks or as further detailed in [Sections 5.6.2](#) and [5.6.3](#).
- w. Testosterone must be collected either at Pre-screening or at screening.

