5.5.2. End-of-Treatment Visit

The EOT Visit should occur within 7 days after pamiparib has been permanently discontinued. Required assessments are listed in [Appendix 1](#). A visit should be scheduled as soon as possible, but the EOT Visit may occur later after discussion with the medical monitor for specific circumstances, such as prolonged hospitalization. The visit at which tumor assessments showed PD may be used as the EOT Visit if all required assessments were performed. Tumor assessments do not have to be repeated if they were performed within 14 days of the EOT Visit or at a prior response evaluation that documented PD. An ECG does not have to be repeated if it was performed within 14 days of the EOT Visit.

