5.6. Follow-Up Phase

5.6.1. Safety Follow-up

All patients who permanently discontinue pamiparib and have not initiated new anticancer therapy will be followed for AEs and SAEs as outlined in [Section 9.3.1](#). Approximately 30 days after the last dose of pamiparib or before initiation of new anticancer therapy, whichever occurs first, the Safety Follow-up Visit will occur with the safety assessments outlined in [Appendix 1](#). If new anticancer therapy is inadvertently initiated before the Safety Follow-up Visit (eg, without the knowledge of the study center team), a Safety Follow-up Visit should be scheduled as soon as possible.

For patients who do not want to or cannot return to the clinic for the Safety Follow-up Visit, the patient should be contacted by telephone for a review of AEs. If these attempts of contact are unsuccessful, the additional attempts detailed in [Section 5.6.3](#) should be made.

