5.6.2. Long-term Follow-up

Patients will be followed for survival and initiation of new anticancer therapy via telephone contact or other means (eg, clinic visit) approximately every 12 weeks ([Appendix 1](#)).

Patients who do not have objective disease progression at the time of pamiparib permanent discontinuation but meet other discontinuation criteria (eg, discontinued for AE and no new anticancer therapy) will continue to have tumor and PSA assessments every 12 weeks and 4 weeks (± 7 days), respectively, until PD or any other reason listed in [Section 5.6.4](#), whichever occurs first. For efficacy assessments as per protocol, refer to [Section 7.3](#) and [Appendix 1](#). If the patient refuses to return for these PSA and tumor assessments or is unable to do so, every effort should be made to contact the patient by telephone to determine the patient's disease status and survival.

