7.3.2. Prostate-Specific Antigen

PSA levels will be collected at timepoints specified in [Appendix 1](#) and tested in a certified local laboratory. In addition, at least, the 3 most recent PSA levels before Day 1 (\geq 1 week between determinations) must be provided to document PSA progression before study entry.

Increases and decreases in PSA will be tracked to assess PSA responses as defined by the PCWG3 criteria described in [Appendix 10](#). A PSA response or progression must be confirmed \geq 3 weeks later.

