#### Time to PSA Progression

Time to PSA progression is defined as the time from the date of the first dose of study drug to the date of a  $\geq 25\%$  increase in PSA with an absolute increase of  $\geq 2$   $\mu\text{g/L}$  above the nadir (or above the baseline for patients with no PSA decline after 12 weeks), confirmed by a second value  $\geq 3$  weeks later. For patients who have not had a PSA progression event as of the data cutoff date, time to PSA progression will be censored at the date of the last PSA assessment. For this secondary efficacy endpoint, the PSA assessments will be summarized for the Safety Analysis Set (Cohorts 1 and 2).

Time to PSA progression will be estimated using the Kaplan-Meier method, and the median time to PSA progression will be presented along with its 2-sided 95% confidence interval using the Brookmeyer and Crowley method. The event-free rate at select timepoints will be calculated along with 2-sided 95% confidence intervals using Greenwood's formula.

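### Patients who stop for PD have no scheduled PSA after the EOT visit, so a first rise close to the last draw is censored unconfirmed and the planned time to PSA progression is biased upward

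*Protocol*

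**What the plan says.** **When PSA is drawn.** Protocol Appendix 1, footnote k: "PSA levels will be assessed during screening, on Day 1, and every 4 weeks (± 7 days), or as clinically indicated". The PSA row has entries at screening, Day 1 of each cycle, unscheduled visits, EOT and long-term follow-up. The Safety Follow-up cell is empty, although hematology and chemistry are entered there.

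**Who continues after EOT.** Footnote k: "Patients without PD at the EOT Visit should be followed with PSA assessments every 4 weeks". Footnote f limits long-term PSA to "Patients who were permanently discontinued from pamiparib for reasons other than PD and meet criteria otherwise", and Protocol 5.6.2 to "Patients who do not have objective disease progression at the time of pamiparib permanent discontinuation".

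**Visit timing.** Protocol 5.5.2: "The EOT Visit should occur within 7 days after pamiparib has been permanently discontinued". The visit that showed PD may itself serve as EOT. Protocol 5.6.1: "Approximately 30 days after the last dose of pamiparib or before initiation of new anticancer therapy, whichever occurs first, the Safety Follow-up Visit will occur".

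**Confirmation and censoring.** Protocol 7.3.2: "A PSA response or progression must be confirmed", with the second value at least 3 weeks later. SAP 6.4.2, for a patient without an event: "time to PSA progression will be censored at the date of the last PSA assessment". The SAP treats duration of PSA response the same way. Neither entry has a rule for a qualifying rise at the last draw.

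**Status of the trial.** SAP Section 8 reports termination after 13 patients, drops all efficacy tables and analyses, and keeps the PSA data as listings to be discussed in the report.

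**The concern.** Kaplan-Meier estimation assumes that a patient censored at a given time has the same later risk as those still followed. Here PSA follow-up ends because the patient has progressed on imaging, while patients without PD keep 4-weekly PSA. Where the first PSA rise appears at about the same time as imaging PD, the schedule removes the draw that would confirm it, and an event becomes a censored observation. The planned event-free rates, and sometimes the median, would then look better than they should.

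The primary endpoint is touched in the other direction. A 50% fall first seen at the last draw also lacks a scheduled confirmation and is scored as non-response.

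**Working it through.** **1. The plan's own PSA figure.** No design figure is stated for time to PSA progression. The only one for PSA is the power for response rate: n = 80, 30% versus 50%, exact binomial, one-sided 0.025. The smallest r with P(X ≥ r | 0.30) ≤ 0.025 is 33, with actual alpha 0.0211. Power is P(X ≥ 33 | 0.50) = 0.9535, against 95% stated. It reproduces.

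**2. The visit calendar.** PSA is drawn on Days 1, 29 and 57. The first scan is at Week 8, taken here as Day 57. Suppose that scan shows PD. EOT is 0 to 7 days after stopping, so by about Day 64.

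| First qualifying rise | Last scheduled PSA | Gap | Outcome |
|---|---|---|---|
| Day 29 | Day 57 or later | at least 28 days | confirmed, event |
| Day 57 | up to Day 64 | 0-7 days, under 21 | censored |
| EOT | EOT | 0 days | censored |

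Only a rise first seen less than 3 weeks before the last draw is lost. A rise at the preceding 4-weekly visit is normally confirmed.

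**3. Would a PSA at Safety Follow-up meet the 3-week rule?** With EOT 0 to 7 days after stopping and Safety Follow-up at 30 days, the gap is 30 − 7 = 23 to 30 − 0 = 30 days, so yes. It can be shorter if EOT is delayed or new therapy brings the visit forward.

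**4. Illustrative size.** The documents give no PSA-progression rate, so the calendar was simulated with 15,000 patients per scenario: PSA every 28 days; scans at Weeks 8, 16 and 24, then every 12 weeks; stop at the first scan showing PD; EOT 0-7 days later; confirmation at least 21 days later. Assumptions from outside the documents: exponential times; median time to PSA rise 60, 90 or 150 days; median time to imaging PD 90 or 150 days; correlation 0, 0.5 or 0.8; every first rise confirmable if redrawn; every patient stops for imaging PD. The last two push the estimated loss up. The comparison is the schedule as written against one confirmatory PSA at least 3 weeks after EOT.

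| | Rises count at any time | Rises count only from Week 12 |
|---|---|---|
| Patients with an unconfirmable rise | 6-18% | 2-8% |
| Excess in event-free rate at about 24 weeks | 3-14 points | 2-9 points |
| Shift in median | 0-28 days in most scenarios (maximum 140) | 0-28 days in most scenarios (maximum 194) |

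The second column is needed because the 12-week qualifier is placed differently in SAP 4.2 and SAP 6.4.2. In SAP 4.2 it can be read as applying to every patient. The 24-week rate was too high in every scenario.

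**5. Lost falls.** If a fraction f of true responses goes unconfirmed, the observed rate under the alternative is 0.50(1 − f). With r = 33 and n = 80:

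- f = 2%: rate 0.490, power 93%
- f = 5%: rate 0.475, power 89%
- f = 10%: rate 0.450, power 78%

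The values of f are assumptions. The effect lowers the response rate and works against the drug.

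**The case against.** The strongest reply is that no biased estimate will be produced: SAP Section 8 cancels every efficacy analysis. That stands, and it confines the point to the planned design and the listings. Time to PSA progression was also a descriptive secondary endpoint with no hypothesis test.

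A reader might infer more than the documents support:

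- **That confirmation is impossible.** It is not. PSA may be drawn when clinically indicated, and the unscheduled-visit column has a PSA entry. Such draws are permitted but not required.
- **That the fastest progressors are all censored.** Unless a Week 12 floor applies, an early riser with a later draw counts as an event. Those lost are patients whose first rise coincides with PD. If PD was called on PSA progression already confirmed, nothing is lost.
- **That the loss can be read from the rPFS medians in Protocol 1.3** (9.8 months biomarker-positive, 2.7 negative). With 1 − exp(−ln 2 × t/median), these give 12% to 38% at Week 8 (t = 56/30.4375 = 1.84 months) and 23% to 61% at Week 16 (3.68 months). Those are chances of an rPFS event, not of a lost PSA event. The upper figures also come from biomarker-negative patients, whom this trial does not enrol.
- **That the gap flatters the primary endpoint.** A lost fall lowers PSA response, which is conservative for a one-sided test.

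None of this supplies the missing scheduled draw or reverses the direction of the bias in the progression endpoint.

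**Conclusion.** The point holds for the planned design. Patients who stop for PD have no scheduled PSA after EOT, and a first qualifying rise less than 3 weeks before the last draw is censored unless someone chooses to repeat the test. The censoring is related to imaging progression and biases time to PSA progression, and similarly duration of PSA response, upward.

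The direction follows from the schedule. The size does not follow from the documents: the simulated ranges rest on the assumptions listed and show only that the 24-week event-free rate is more exposed than the median. For the 13 enrolled patients the remaining risk is one of reading: in the listings, a final rise or fall without a repeat draw could be taken as no progression or no response.

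**What to change.** 1. **Appendix 1:** add a PSA to the Safety Follow-up column for all patients, at least 3 weeks after the EOT PSA and before new anticancer therapy where possible.
2. **SAP 6.4.2:** keep one definition of PSA progression for all patients. Add a sensitivity analysis that counts an unconfirmed qualifying rise at the last PSA as an event. Do not waive the 12-week qualifier only for patients stopped for imaging PD, because the event definition would then depend on imaging outcome.
3. **Final report:** in the PSA listings, flag any final rise or fall that had no confirmatory draw. This is the only step still relevant to the trial as it ended.

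The cost is one extra PSA test per patient (about 100 at the planned size) and a short SAP addition. The visit already draws blood, but PSA is tested locally and safety blood centrally where available, so a separate tube may be needed.

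The limits are these. The confirming value is taken off drug. It may still be missing if new therapy starts early or the visit is by telephone. If rises count only from Week 12, it does not rescue a patient who stops on Day 57: Safety Follow-up falls at about Day 87, which gives only one value after Week 12 (Day 85).
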